7.1.3. GSK3228836 Drug Induced Kidney Injury (Renal) Stopping Criteria

If any of the following are observed, results should be confirmed, and if confirmed, further evaluation for alternative causes should be pursued in consultation with the Medical Monitor:

- Persistent ACR ≥0.03 mg/mg (≥30 mg/g)
- Blood in urinalysis ≥5 red blood cells (RBC) per high power field (HPF) confirmed by urine microscopy
- Persistent elevation of serum creatinine (>26.52 μmol/L or 0.3 mg/dL change from baseline)

Following confirmation of the criteria above, further evaluation may include but not be limited to a 24-hour urine analysis, consultation with a nephrology specialist, renal ultrasound, urine microscopy, serum urea and creatinine, platelet count, urgent serum vasculitis screen (including ANCA, antinuclear antibody [ANA], double stranded deoxyribonucleic acid [dsDNA], cryoglobulins), serum protein electrophoresis (SPEP)/urine protein electrophoresis (UPEP), and complement panel (C3, C4, C5a, and Bb). Further evaluation and actions should be determined by the investigator in consultation with the Medical Monitor.

Treatment Hold/Treatment Discontinuation

- Hold study treatment in participants who develop ACR ≥0.5 mg/mg (500 mg/g), or eGFR >25% reduction from pre-dose range, pending consultation with the Medical Monitor and further evaluation of the cause.
 - If a dose is held, once eGFR increases to within baseline, ACR decreases to <0.5 mg/mg (500 mg/g), or the underlying cause of the decline in renal

function is corrected, weekly dosing may be reinitiated after consultation with the Medical Monitor

- Participants must be monitored weekly until ACR or eGFR resolve, stabilize, or return to within pre-dose range
- Hold study treatment in participants with ACR ≥ 2 mg/mg (2000 mg/g), perform further evaluation for acute glomerulonephritis, as clinically indicated. If acute glomerulonephritis is confirmed or probable (i.e., meets clinical definition of rapidly progressive glomerulonephritis [RPGN] if biopsy not feasible), GSK3228836 should be permanently discontinued
 - Participants must be monitored weekly until ACR resolves, stabilizes, or returns to within baseline values
- Delay in treatment of suspected RPGN should be avoided.

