7.1.4. GSK3228836-Induced Vascular Inflammation and Complement Stopping Criteria

If any of the following are observed, results should be confirmed with a repeat sample collection and analysis, and if confirmed, further evaluation for alternative causes should be pursued in consultation with the Medical Monitor.

Repeat sample collection of C3, C4, Bb, C5a would be triggered by changes in the clinical signs and symptoms of complement activation (≥ 2 + haematuria; increasing urine ACR; vasculitic or purpuric rash; peripheral neuropathy; jaundice). Additional complement analyses for example CH50, Factor B level, Factor H level, sC5b-9 should also be considered in discussion with the Medical Monitor and Safety Panels.

- **Persisting & deteriorating longitudinal trends in change from baseline for C3 and/or C4 defined as:**
 - If participant's baseline C3 and/or C4 is *within* the lab's normal range at baseline: there is a sequential decline in C3 and/or C4 once levels have fallen below LLN for ≥ 4 weeks OR
 - If participant's baseline C3 and/or C4 is *below* the lab's LLN at baseline: there is further sequential decline in C3 and/or C4 for ≥ 4 weeks OR
 - Regardless of baseline C3 and/or C4 level: there is a $\geq 80\%$ *reduction* in the participant's C3 and/or C4 level at any point AND
 - There is an associated ≥ 3 -fold *increase* in Bb and/or C5a from participant's baseline OR
 - There are associated biochemical sequelae for example, a rising high sensitivity C-reactive protein (hs-CRP); rising monocyte chemoattractant protein (MCP-1); new thrombocytopenia, new renal impairment with no other explanation such as intercurrent infection OR

- There are associated clinical sequelae, for example, ≥ 2 + haematuria; increasing urine ACR; vasculitic or purpuric rash; peripheral neuropathy; jaundice OR
- There is new cANCA or pANCA positivity
- **Persisting & deteriorating longitudinal trends in change from baseline for Bb and/or C5a where**
 - There is a ≥ 3 -fold increase in Bb and/or C5a over baseline AND
 - This is persisting or increasing week on week in sequential data plots OR
 - There are associated biochemical sequelae for example, a rising hs-CRP; rising MCP-1, new thrombocytopenia, new renal impairment with no other explanation such as intercurrent infection OR
 - There are associated clinical sequelae, for example, ≥ 2 + haematuria; increasing urine ACR, vasculitic or purpuric rash; peripheral neuropathy; jaundice or any combination of these OR

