4.5.3. Additional Safety Assessments

4.5.3.1. Laboratory Data

Only central lab data will be used for summary analyses and figures; local lab data will be included in listings, as appropriate.

If normal LAB ranges are collected and there are duplicate LAB records at the same date/timepoint, the “worst-case” value will be selected. Specifically:

- For LAB result > Lower Normal range, select Maximum of Lab result (AVAL).
- For LAB result \leq Lower Normal range, select minimum of Lab result (AVAL).

For virology LAB parameters, if time information is missing from collection and from the test performed, the maximum lab value should be selected. If first run has values outside acceptance criteria, and the sample was re-run, the latest LAB result should be selected by the vendor.

Summary statistics for changes from baseline for each numeric parameter at each visit will be presented, separately for all clinical chemistry parameters, all haematology parameters, and all urinalysis parameters.

For immunology parameters, summary statistics for actual value and change from baseline data for each parameter at each visit will be presented, separately for all numeric parameters. Listings will also be created.

For categorical immunology parameters c-ANCA and p-ANCA, summary table of baseline Negative to post-baseline Positive, baseline value no change, and baseline Positive to post-baseline Negative will be created. Listing will be created as well.

For coagulation parameters prothrombin international normalised ratio (INR), prothrombin time (PT_{test}) and activated partial thromboplastin time (aPTT), summary statistics for actual at each visit will be presented. Listing will be created as well.

Shift tables for laboratory parameters showing baseline toxicity versus maximum post-baseline (on-treatment and off-treatment periods combined) toxicity for each grade (Grade1, Grade 2, etc.) for chemistry and haematology parameters will be provided.

Increase to Grade 3 or higher lab abnormalities for platelets, ALT, aspartate aminotransferase (AST), INR, total bilirubin, serum creatinine, eGFR, albumin to creatinine ratio (ACR) will be summarized.

Laboratory values outside of normal range will be summarized and listed.

Grading categories for laboratory tests are determined using the DAIDS grading system Version 2.1 [[National Institute of Allergy and Infectious Diseases. Division of AIDS, 2017](#)].

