Summary of post-baseline hepatobiliary laboratory abnormalities will be provided.

The worst-case urinalysis results post-baseline (on-treatment and off-treatment periods combined) relative to baseline will be summarized.

Summaries of result shifts from baseline, worst-case results post-baseline relative to baseline, and results with increase to \geq maximum toxicity grade post-baseline for chemistry, haematology, urinalysis, and immunology as applicable, will also be presented for treatment with GSK3228836 and PegIFN separately, by treatment arm and in total within each treatment period.

GSK3228836 liver chemistry monitoring and stopping event reporting will be summarized and listed. The liver monitoring and stopping criteria are described in the protocol Section 7.1.1.

GSK3228836 haematological monitoring and stopping events will be summarized and listed based on laboratory parameters (platelet count and anti-platelet antibodies). The haematological stopping criteria are described in the protocol Section 7.1.2.

GSK3228836 drug induced kidney injury (renal) monitoring and hold or stopping events will be identified programmatically and will be summarized and listed based on laboratory parameters (ACR, urinalysis red blood cells (RBC), serum creatinine, and eGFR). The kidney injury monitoring and stopping criteria are described in the protocol Section 7.1.3.

Drug induced vascular injury and complement monitoring/stopping event will be summarized and listed based on laboratory parameters (C3, C4, Bb, C5a, hs-CRP, MCP-1, p-ANCA, c-ANCA, eGFR, bilirubin, and platelet count). The drug induced vascular injury and complement monitoring and hold/stopping criteria are described in the protocol Section 7.1.4.

Hold/stopping event profile for GSK3228836 will be provided for any subject who has met hold or stopping criteria specified in protocol Section 7.1. Relevant information will be reported, including baseline characteristics, AEs/SAEs, concomitant medication, medical history/current medical conditions, study treatment administration details, laboratory values, and individual line plots of complement (C3/C4/C5a/Bb), inflammatory markers (hs-CRP/MCP-1), serum creatinine/creatinine clearance or eGFR/ACR, and platelet count.

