6.2.4. Multiple Measurements at One Analysis Time Point

Table 15 Multiple Measurements at One Analysis Time Point

Definition

 • Handling of multiple measurements within an analysis window for primary endpoint is described in Section 4.2.2 • Assessments on unscheduled visit will not be included in the tables of summary statistics by visit but will be included in the associated listings. Also, such assessments on unscheduled visit will be used for the "any time on-treatment" or "Any visit post-baseline" time point. • If there are multiple assessments on scheduled visit within visit window, will query the site to identify the valid assessment as the assessment for the scheduled visit. • Participants having both High and Low values for Normal Ranges at any post-baseline visit for safety parameters will be counted in both the High and Low categories of "Any visit post-baseline" row of related summary tables. • If after window assignment of Early Termination visits there are multiple valid assessments of a parameter within the same window (see Section 6.2.8), then the following hierarchy will be used to determine the value to be used for summary statistics of observed values: 
 ○ the assessment closest to the window target Study Day. ○ if there are multiple assessments equidistant from the target Study Day, then the mean of these values will be used. • If normal LAB ranges are collected and there are duplicate LAB records at the same date/timepoint, the the "worst-case" value will be selected. Specifically: 
 ○ For LAB result > Lower Normal range, select Maximum of Lab result (AVAL). ○ For LAB result <= Lower Normal range, select minimum of Lab result (AVAL).

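### The SAP's worst-case rule for duplicate laboratory records ignores direction of harm: it keeps the better of two in-range values where a fall is harmful, and gives two answers for pairs that straddle the lower limit of normal

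*SAP*

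**What the plan says.** SAP 4.5.3.1 (Laboratory Data) gives a rule for cases where normal ranges are collected and "there are duplicate LAB records at the same date/timepoint". It calls the selected value worst-case and defines it in two bullets:

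- above the lower limit of normal: "For LAB result > Lower Normal range, select Maximum of Lab result (AVAL";
- at or below it, as also worded in Table 15 of SAP 6.2.4: "For LAB result <= Lower Normal range, select minimum of Lab result (AVAL".

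Neither place distinguishes analytes by whether a high or a low value is harmful, and neither says what to do when the duplicates fall on opposite sides of the limit. The SAP version history gives clarity for programming as the reason for adding the rule.

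The rule sits in the section that governs the safety laboratory outputs: "Only central lab data will be used for summary analyses and figures". Those outputs include change from baseline by visit, worst-case post-baseline results relative to baseline, and summaries described as "Increase to Grade 3 or higher lab abnormalities for platelets, ALT", a list that goes on to name eGFR. For the renal criteria the same section says that "monitoring and hold or stopping events will be identified programmatically", using ACR, urinalysis red cells, serum creatinine and eGFR. One of those criteria, in Protocol 7.1.3, is relative to the participant's own values: "eGFR >25% reduction from pre-dose range".

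**The concern.** Taking the maximum is the worst case only when a high value is harmful. For platelets, neutrophils, haemoglobin, C3, C4, albumin and eGFR the harm is a fall, so for two in-range duplicates the rule does the opposite of what its label promises. A pair with one value on each side of the limit satisfies both bullets, and two programmers could follow the text faithfully and produce different datasets.

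At stake is the accuracy of safety tables that readers will take to be conservative. Platelets, renal function and complement all have their own monitoring and stopping criteria in Protocol 7.1. A fall within the normal range would appear smaller than it was. A criterion defined as a percentage fall can be met without the value leaving the normal range, so it is the kind most exposed to this rule.

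**Working it through.** The plan states no figure for this rule, so there is none to reproduce. The check applies the two bullets to pairs of duplicates and compares the value kept with the minimum, which is the true worst value where low is harmful. The documents give no numeric LLN, so every LLN, baseline and pair below is assumed for illustration. The thresholds come from Protocol 7.1.2 (platelets <100 x10^9/L), 7.1.3 (eGFR fall >25%), 7.1.4 (C3/C4 fall of at least 80%) and 7.2.1 (ANC <750 cells/mm3, haemoglobin <8.5 g/dL).

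Percentage change = (kept value / pre-dose value - 1) x 100.

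**Both duplicates above the limit: maximum kept**

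- eGFR, pre-dose 120, duplicates 88 and 95, any LLN below 88. Kept: 95/120 - 1 = -20.8%, criterion not met. Worst: 88/120 - 1 = -26.7%, criterion met.
- Platelets, baseline 300, duplicates 160 and 240, LLN 130 to 150. Kept: 240/300 - 1 = -20.0%. Worst: 160/300 - 1 = -46.7%. The fall is understated, but neither value crosses a platelet threshold.

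A 25% eGFR fall stays in range when 0.75 x pre-dose > LLN, that is, when pre-dose > LLN/0.75. This gives pre-dose > 80 for an LLN of 60, and > 120 for an LLN of 90. Protocol 5.2 excludes a GFR below 60, so pre-dose values above these cut-points are admissible.

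**Both duplicates at or below the limit: minimum kept**

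- Platelets 95 and 110 (LLN 130 to 150): 95 kept, <100 met.
- Haemoglobin 8.3 and 9.0 (LLN 12): 8.3 kept, <8.5 met.
- ANC 0.7 and 0.9 x10^9/L (LLN 1.5): 0.7 kept, <0.75 met.
- C3 0.25 and 0.35 g/L, baseline 1.5 (LLN 0.8): 0.25 kept, 0.25/1.5 - 1 = -83.3%, the 80% fall met.

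The worst value survives in each case. The C3/C4 trend criterion for participants with an in-range baseline, "sequential decline in C3 and/or C4 once levels have fallen below LLN", also operates in this region.

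**One duplicate on each side of the limit: both bullets apply**

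- Platelets 95 and 160, LLN 130, 140 or 150. Applying the first bullet keeps 160 and loses the count below 100. Applying the second keeps 95. The text does not choose.
- eGFR 88 and 95 with an LLN of 90 becomes such a pair: either 95 (-20.8%) or 88 (-26.7%).

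**The case against.** A reader might infer that the rule hides low platelets, neutrophils, haemoglobin or complement in general. The documents do not support that. The second bullet keeps the minimum at or below the limit, and on the assumed limits the absolute thresholds for platelets, ANC and haemoglobin lie there. When both duplicates are low, nothing is lost. The platelet pair 95 and 160 is not a clear loss either, because one reading of the text keeps 95. This part of the objection stands and limits the point to in-range and straddling pairs.

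The eGFR illustration is also open to challenge:

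- The rule applies only where a normal range is collected, and no document says one is collected for eGFR. Protocol Table 17 lists creatinine but not eGFR, and Protocol 5.2 describes GFR as calculated by formula.
- If eGFR is derived after creatinine has been de-duplicated, keeping the maximum in-range creatinine gives the lowest eGFR, which is the conservative direction.
- The SAP does not say whether the programmatic renal events use de-duplicated records or all records.
- The protocol criterion refers to a pre-dose range, whereas the illustration uses a single pre-dose value.

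These points stand and make the missed renal event conditional. They do not affect the other analytes where low is harmful.

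Other safeguards exist. Table 15 sends multiple assessments on a scheduled visit to the site as a query, which may leave few pairs for this rule. Values outside the normal range are summarised and listed, and participants with both high and low post-baseline values count in both categories. Hold and stopping profiles include laboratory values and line plots. These reduce the likely effect, but they neither make the maximum the worst case for an in-range fall nor settle a straddling pair.

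**Conclusion.** The point holds in a limited form. Followed as written, the rule contradicts its own label when both duplicates are above the limit and a fall is the harm, and it is undefined when the pair straddles the limit. The first defect understates in-range falls in change-from-baseline and worst-case summaries. Absolute low thresholds are exposed only through straddling pairs, on the assumption that those thresholds lie below the laboratory's LLN.

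A missed >25% eGFR reduction is possible but not demonstrated. It requires that a normal range is collected for eGFR, that de-duplicated eGFR records feed the renal event outputs, and that both duplicates are in range (or a straddling pair is resolved upwards). Complement is less exposed on the criteria checked above. However, the hold and discontinuation rules at the end of Protocol 7.1.4 speak of decreased C3/C4 without naming a limit, so an in-range fall could bear on those outputs too.

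The overall size cannot be computed, because neither the number of duplicates nor any LLN is stated. A reader might also infer a risk to participants' dosing decisions. For platelets the documents point the other way: Protocol 1.3 and 10.2 require a local count to be available before each GSK3228836 dose, while this rule governs analysis records and the summaries use central data. This is a minor reporting defect that is worth correcting because the correction costs so little.

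**What to change.** Replace the two bullets in both SAP 4.5.3.1 and Table 15 with selection by each analyte's adverse direction:

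- minimum where low is harmful (platelets, neutrophils, haemoglobin, eGFR, C3, C4, albumin);
- maximum where high is harmful (ALT, AST, bilirubin, creatinine, ACR, INR, Bb, C5a, hs-CRP, MCP-1);
- both values retained, for separate worst-low and worst-high tables, where either direction is harmful.

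This also resolves straddling pairs, since the choice no longer depends on the limit of normal. For the same reason it can be applied to analytes without a collected range, and the text should say so. State as well whether eGFR is derived before or after de-duplication, and whether the programmatic hold and stopping events use all records or the selected ones.

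Under the new rule the eGFR pair 88 and 95 yields 88 (-26.7%), the in-range platelet pair 160 and 240 yields 160 (-46.7%), and the straddling pair 95 and 160 yields 95. The pairs with both values at or below the limit do not change. The cost is a lookup table in the programming specification and a few lines of SAP text, with no new data collection.

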HBeAg (for participants HBeAg positive at screening)		X	X	X	X		X		X		X		X		X		X		X		X		X		X

PegIFN Dosing Week	1 ^a	2	3	4	5	6	7	8	9	10	11	12	13	14	15	16	17	18	19	20	21	22	23	24	
Window	±3 days																								
Complement C3, C4, C5a, Bb, hs-CRP, MCP-1			X		X				X					X			X				X				
ANCA, Ang II		X			X				X					X			X				X				
PK – PegIFN		X	X		X									X			X				X				
PK –GSK3228836		X		X							X			X											
HBV RNA, and sequencing (HBV genotype/phenotype; HBV DNA and/or RNA)		X	X		X			X		X				X			X				X				X
HBcrAg		X			X				X					X							X				
PBMC Collection for immunophenotyping ⁵		X			X									X											
Soluble Protein (immunology)		X	X		X									X			X				X				
PAXGene RNA for expression analysis in whole blood		X			X									X											
Archived Samples [serum; plasma]		X	X	X	X			X		X				X			X				X				X

- a. The first planned PegIFN visit occurs 7 days after the planned GSK3228836 dosing period.
- 1. Assessment of PegIFN eligibility should be based upon pre-dose safety assessments and laboratory assessments from previous visit
- 2. For specific Peg-IFN eligibility criteria please refer to protocol Section 4.1; **If ineligible for PegIFN refer to Table 5.**
- 3. If consistent with local regulations, participants are permitted to self-administer PegIFN at home, site staff may call to assess the participant by phone at this visit and no clinic visit is required. If local regulations or practices prefer to administer PegIFN within the clinic, this can be a clinic visit.
- 4. Participants in Japan are expected to return for a mid-week haematology assessment during Week 1 and at Week 5 and 7 in accordance with local regulations
- 5. Only for selected sites able to transport to the analysis lab as specified in the SRM

Table 5 Reassessment of PegIFN Eligibility

If a participant is ineligible for PegIFN dosing immediately (Week 1, [Table 4](#)), complete the SoA of PegIFN Eligibility Week 1, [Table 5](#).

Eligibility for PegIFN will be reassessed following the SoA in [Table 5](#) on PegIFN Eligibility Week 2, 3, 4, 6, 8, 10 and 13.

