9.4.1. General Considerations

Unless otherwise specified, baseline will be the last value/assessment before the first dose of study treatment (Day 1 pre-dose). If there are multiple assessments collected at the same scheduled time, the average of these assessments will be used as the baseline.

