4.1.2. Baseline Definition

For all endpoints (except as noted in baseline definitions) the baseline value will be the latest pre-dose assessment with a non-missing value, including those from unscheduled visits. If time is not collected, Day 1 assessments are assumed to be taken prior to first dose and used as baseline. If there are multiple assessments collected at the same scheduled time, the average of these assessments will be used as the baseline.

Unless otherwise stated, if baseline data is missing no derivation will be performed and baseline will be set to missing.

Baseline of estimated glomerular filtration rate (eGFR) is defined as the mean of all pre-dose values, from screening to Day 1 pre-dose assessment.

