6.2.2. Study Phase and Period

Safety assessments and events will be classified according to the time of occurrence relative to the study intervention period.

Table 13 Study Phase Definitions

Study Intervention Phase	Definition
Pre-Treatment	For Assessments – Date ¹ ≤ Study Treatment Start Date For Events – Date ¹ < Study Treatment Start Date
On-Treatment	For Assessments – Study Treatment Start Date < Date ¹ < Last Treatment Stop Date + 7 days For Events – Study Treatment Start Date ≤ Date ¹ < Last Treatment Stop Date + 7 days
Post-Treatment	Date ¹ ≥ Last Treatment Stop Date + 7 days

¹ Date is the start date of the assessment/event.

Table 14 Study Period Definitions

Study Intervention Period	Definition
GSK3228836 Treatment Period	For Assessments – All Analysis Timepoints within : WK 1 DAY 1 to a day prior PEGIFN ELIGIBILITY WK 1 DAY 1* For Events – Study Treatment Start Date ≤ Date ¹ < GSK836 Last Treatment Date + 7 days
PegIFN Eligibility Period	For Assessments – All Analysis Timepoints within : 1) PEGIFN ELIGIBILITY WK 1 DAY 1 to a day prior PEGIFN DOSING WK 1 DAY 1* and 2) PEGIFN ASSESSMENT WK 14 to a day prior OT-W1 OT-DAY 1*

Study Intervention Period	Definition
	For Events – $GSK836 \text{ Last Treatment Date} + 7 \text{ days} \leq \text{Date}^1 < \text{PegIFN Treatment Start Date}$ *if subject withdrew or never received PegIFN dosing before PegIFN Dosing Visit then end of period would be 'Last PegIFN Assessment Week Stop Date + 7 days'
PegIFN Treatment Period	For Assessments – All Analysis Timepoints within : PEGIFN DOSING WK 1 DAY 1 to a day prior OT-W1 OT-DAY 1* For Events – $\text{PegIFN Treatment Start Date} \leq \text{Date}^1 < \text{PegIFN Treatment Stop Date} + 7 \text{ days}$
Follow-up Period	For Assessments – All Analysis Timepoints within : OT-W1 OT-DAY 1* onwards For Events – If subject never received PegIFN dosing and did not discontinue on-treatment - $\text{Date}1 \geq \text{Last PegIFN Assessment Week Stop Date} + 7 \text{ days}$ Else $\text{Date}1 \geq \text{Last Treatment Stop Date} + 7 \text{ days}$

¹ Date is the start date of the assessment/event.

* If a subject withdrew early or skipped period(s), consider start of next period analysis timepoint. If analysis timepoint is not collected, use corresponding planned start visit day in Section 6.2.8.

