6.2.3. Study Day and Reference Dates

The study reference date is the study treatment start date and will be used to calculate study day for safety and efficacy measures.

The study day is calculated as below:

- Assessment Date = Missing → Study Day = Missing
- Assessment Date < Reference Date → Study Day = Assessment Date – Reference Date
- Assessment Date ≥ Reference Date → Study Day = Assessment Date – Reference Date + 1

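### The PegIFN-period laboratory shift and grade-increase tables have no PegIFN baseline; by default they use one taken before GSK3228836, which misclassifies abnormalities in both directions

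*SAP*

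**What the plan says.** SAP 4.5.3.1 plans shift-from-baseline, worst-case-versus-baseline and toxicity-grade-increase summaries for chemistry, haematology, urinalysis and immunology. It adds that these "will also be presented for treatment with GSK3228836 and PegIFN separately, by treatment arm and in total within each treatment period". The sentence does not say which baseline the PegIFN tables use.

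The general rule is in SAP 4.1.2: "For all endpoints (except as noted in baseline definitions) the baseline value will be the latest pre-dose assessment with a non-missing value". Where no time is collected, "Day 1 assessments are assumed to be taken prior to first dose and used as baseline". Protocol 9.4.1 agrees: "baseline will be the last value/assessment before the first dose of study treatment (Day 1 pre-dose"). The one listed exception does not help: "Baseline of estimated glomerular filtration rate (eGFR) is defined as the mean of all pre-dose values, from screening to Day 1 pre-dose assessment". SAP 6.2.3 likewise has a single anchor: "The study reference date is the study treatment start date and will be used to calculate study day for safety and efficacy measures".

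For assessments, SAP Table 14 (section 6.2.2) defines the PegIFN Treatment Period as "PEGIFN DOSING WK 1 DAY 1 to a day prior OT-W1 OT-DAY 1". The visit at which PegIFN is started is therefore inside the period. On timing, a footnote to protocol Table 4 states: "The first planned PegIFN visit occurs 7 days after the planned GSK3228836 dosing period".

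Adverse events follow a different rule. SAP 4.5.2 places an event in the PegIFN period when its onset is on or after the PegIFN start date.

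**The concern.** In a sequential regimen, a reader will use the separate PegIFN tables to see what changed once PegIFN began. With a baseline taken before GSK3228836, they show what changed since before either drug, sampled during the PegIFN period. That is a different quantity.

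The difference matters most where the two drugs overlap. Protocol 2.3.1 expects ALT flares with both GSK3228836 and PegIFN. It describes gradual platelet decline for the antisense class and platelet decreases with PegIFN. A raised ALT or low platelet count at the end of GSK3228836 that is unchanged at PegIFN start would appear in the GSK3228836 tables and again as a shift in the PegIFN tables.

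The SAP would then also disagree with itself. An ALT-increase adverse event that began on GSK3228836 stays out of the PegIFN period under the onset rule, while the same persisting ALT value enters the PegIFN shift table.

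**Working it through.** This is a question of definitions, and the plan states no figure of its own for it. Three checks apply.

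**1. Age of the baseline when PegIFN starts.** SAP Table 19 gives the target study day of PegIFN Dosing Week y, after z ineligible weeks, as 1 + 7 × (23 + y + z) in Arm 1, with 11 in place of 23 in Arm 2. To confirm the reading, set y = 24 and z = 0. This gives 1 + 7 × 47 = 330 and 1 + 7 × 35 = 246, the end-of-treatment target days in SAP Tables 2 and 3.

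PegIFN start is y = 1. The latest permitted start, at Eligibility Week 13, has z = 12.

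| Arm | Start | Study day | Days since Day 1 | Weeks |
|---|---|---|---|---|
| 1 | undelayed (z = 0) | 1 + 7 × 24 = 169 | 168 | 24 |
| 1 | latest (z = 12) | 1 + 7 × 36 = 253 | 252 | 36 |
| 2 | undelayed (z = 0) | 1 + 7 × 12 = 85 | 84 | 12 |
| 2 | latest (z = 12) | 1 + 7 × 24 = 169 | 168 | 24 |

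The baseline is thus 12 to 36 weeks old at PegIFN start, and older at each later PegIFN visit.

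**2. Effect of the baseline on the grade-increase flag.** A PegIFN-period increase is flagged when the maximum grade on PegIFN exceeds the baseline grade. The grades below are illustrative.

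| Day 1 / last before PegIFN / maximum on PegIFN | Flagged, Day 1 baseline | Flagged, PegIFN baseline |
|---|---|---|
| 0 / 0 / 2 | yes | yes |
| 0 / 2 / 2 | yes | no |
| 0 / 2 / 3 | yes, as a rise of three grades | yes, as a rise of one grade |
| 1 / 0 / 1 | no | yes |
| 2 / 0 / 2 | no | yes |

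In 0/2/2 nothing worsened after PegIFN began, yet an increase is shown. In 2/0/2 the grade worsened by two on PegIFN, yet no increase is shown.

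**3. Whether the protocol leaves room for this.** The limits at study entry and at PegIFN start are:

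| Parameter | Study entry (protocol 5.1, 5.2) | PegIFN start (protocol 5.3, Table 8) |
|---|---|---|
| ALT | at most 2 × ULN | below 5 × ULN |
| Platelets (× 10⁹/L) | at least 140 | above 90 |

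A participant can therefore reach the first PegIFN dose with ALT or platelets already moved from Day 1. Protocol 5.3 also provides for PegIFN in some participants whose GSK3228836 was held or reduced under the liver criteria.

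SAP Table 14 adds to the problem. A Dosing Week 1 Day 1 sample drawn before the first PegIFN dose falls inside the PegIFN period, so a value with no PegIFN exposure can supply the period's worst case.

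**The case against.** The strongest reply has four parts.

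**The Day 1 baseline is an inference.** SAP 4.5.3.1 names no baseline for the period tables, protocol 9.4.1 allows for exceptions specified elsewhere, and the SAP leaves output detail to a programming specification that is not among the documents. This stands as a limit on certainty. However, the SAP does not point to that specification for a period baseline, and its own rule covers all endpoints.

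**Other outputs carry the information.** Laboratory values are summarised by visit, and chemistry and haematology are drawn at PegIFN Week 1, so levels at PegIFN start can be seen. SAP 4.5.3.1 also summarises PegIFN dose-modification criteria that need no baseline, such as ALT above 5 and above 10 × ULN. Drug attribution of adverse events rests with the investigator. Table 14 keeps the waiting time of a delayed start in a separate eligibility period. All of this lessens the harm. None of it corrects the participant-level shift tables.

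**A new baseline would not separate the drugs.** Protocol 4.3 gives GSK3228836 a half-life of about 3 weeks. At an undelayed start, 7 days after the last dose, 0.5^(7/21) = 79% of the drug level remains; at the latest start, 91 days after, 0.5^(91/21) = 5% remains. This stands. A PegIFN baseline shows change since PegIFN began, which is not the same as change caused by PegIFN.

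**Day 1 is a defensible reference for the regimen as a whole.** It is, and replacing it outright could hide a persisting flare. That is a reason to keep both versions.

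**Conclusion.** The point holds as a gap in definition. No baseline is set for the PegIFN-period tables, and the default rule puts it before GSK3228836, 12 to 36 weeks before PegIFN starts. Misclassification can go either way, and the laboratory tables are then at odds with the onset rule for adverse events. It rests on the general baseline rule governing these tables; a period baseline in the programming specification would reduce the point to one missing SAP sentence. It is worth fixing, but it touches no primary or secondary efficacy result.

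A reader might infer more than the documents support:

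- **That the tables overstate PegIFN toxicity.** The 2/0/2 pattern shows they can also understate it. The net direction is unknown.
- **That the longer GSK3228836 arm is worse affected.** This is plausible, but what matters is abnormality unresolved at PegIFN start, and nothing is given on that by duration.
- **That carried-over platelet falls are capped at 36%.** The figure (140 − 90)/140 = 35.7% applies to someone entering exactly at 140. From an illustrative 250, the fall to 90 would be (250 − 90)/250 = 64%.
- **That the number of miscounted participants can be derived.** There are no laboratory results, and the grading cut-offs are not reproduced.

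**What to change.** 1. In SAP 4.1.2, add a PegIFN baseline: the last non-missing value before the first PegIFN dose. State how a same-day sample without a recorded time is treated, as is already done for Day 1. Say whether eGFR keeps its own averaging rule.
2. In SAP 4.5.3.1, use this baseline for the PegIFN-period shift, worst-case and grade-increase tables. Keep the Day 1 version alongside, and keep Day 1 for the GSK3228836-period and overall tables.
3. In SAP Table 14, state that samples taken before the first PegIFN dose, including the Dosing Week 1 Day 1 pre-dose sample, are not PegIFN-period post-baseline values. Without this, one sample could serve as both baseline and outcome.
4. Add a footnote to the new tables saying that they show change since PegIFN start and that GSK3228836 may still be present.

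The cost is one derived baseline flag, some additional tables and a few sentences of SAP text. The samples are already in the Schedule of Activities; no visit or design change is needed.
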